3. STUDY DESIGN

3.1. Overall Study Design and Flow Chart

This study will be an open-label, 3-period, 3-treatment, fixed-sequence study in healthy subjects (males and females of non-childbearing potential), performed at a single Clinical Unit.

The study will comprise of the following periods (visits):

- A Screening Period of maximum 28 days (Visit 1);
- A fixed sequence of 3 Treatment Periods during which subjects will be resident at the Clinical Unit from one day prior to administration of verinurad+allopurinol (Day -1) of Treatment Period 1 until the morning of Day 5 of the Treatment Period 2, and similarly between Day -1 to Day 5 of Treatment Period 3. There will be a washout period of 14

days between Treatment Periods 2 and 3 dosing. The 3 Treatment Periods, including the washout period, will be a total of up to 36 days (Visits 2 to3);

• A Follow-up Visit within 7 to 14 days after the last administration of verinurad+allopurinol (Visit 4).

Subjects will be resident at the Clinical Unit from Day -1 of Treatment Period 1 (Visit 2), ie, prior to the evening meal the night before first dosing with verinurad+allopurinol, until the morning of Day 5 of Treatment Period 2, ie, at least 96 hours after the second dosing with verinurad+allopurinol. There will be no washout between Treatment Period 1 and Treatment Period 2. Subjects will be resident continuously for the full duration of Treatment Periods 1 and 2. There will be a minimum washout period of 14 days between dosing in Treatment Period 2 and dosing in Treatment Period 3. Subjects will not be required to be resident at the Clinical Unit for around 10 days during the washout period. Subjects will be resident again from Day -1 of Treatment Period 3 (Visit 3), ie, prior to the evening meal the night before third (last) dosing with verinurad+allopurinol, until the morning of Day 5 of Treatment Period 3, ie, at least 96 hours after the last dosing with verinurad+allopurinol. The subjects will return for a Follow-up Visit in 7-14 days after the last verinurad+allopurinol dose.

Each subject will receive a single dose of verinurad+allopurinol on 3 occasions, under fasted conditions. Each subject will also receive a single dose of cyclosporine on 1 occasion and a single dose of rifampicin on 1 occasion, with cyclosporine and rifampicin being dosed on separate occasions and always together with verinurad+allopurinol.

Details on IMP administration is provided in Section 5.4.3.

Figure 3-1 Study Flow Chart

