10. EVALUATION AND CALCULATION OF VARIABLES

10.1. Safety Variables

10.1.1. Adverse Events

All AEs will be coded using the latest version of the MedDRA vocabulary, and will be listed for each subject.

Adverse events will be assigned to a treatment based on the start date/time of the AE in relation to dosing in that treatment period; for tabulation purposes the AE will then be assigned to the treatment received in the respective treatment period as follows:

- Treatment Period 1: AEs with start date/time at the time of or after dosing in Treatment Period 1 until the time of dosing in Treatment Period 2.
- Treatment Period 2: AEs with start date/time at the time of or after dosing in Treatment Period 2 until the time of dosing in Treatment Period 3.
- Treatment Period 3: AEs with start date/time at the time of or after dosing in Treatment Period 3 until the Follow-up Visit,

Adverse events with missing start dates/times will be handled as follows:

- Adverse events with unknown start times, but with start date known, will be imputed with a time of 00:00, unless the start date corresponds to any given dosing date. In this case the start time will be imputed with the time of dosing. If this results in a start date/time after end date/time of the AE, then the time will also be imputed with 00:00.
- Adverse events with completely unknown start dates will be imputed with the date and time of dosing, unless the end date is known and prior to dosing; in that case the start date will be imputed as the date of Screening and a time of 00:00.
- Adverse events with partially known start dates/times will be treated as follows:
 - If only the day is missing, then the day will be imputed with the first day of the month, unless the month and year in which the AE started is a month and year in which IMP was administered, then the day will be imputed with the first day on which IMP was administered in that month. If this results in a start date after the end date, then the day will be imputed with the first day of the month.
 - If only the month is missing and the year is a year in which IMP was administered, then the month will be imputed with the first month in which IMP was administered. If this results in a start date after the end date of the AE, then the month will be imputed with JAN. If the known year part is not a year in which IMP was administered, then the month will also be imputed with JAN.

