 - If both the day and month is missing and the year is a year in which IMP was administered, then the day and month will be imputed with the day and month of dosing. If this results in a start date after end date, then the day and month will be

imputed with 01JAN. If the year is not a year in which IMP was administered, then the day and month will also be imputed with 01JAN.

- If only the year is missing, then the year will be imputed with the year of dosing.

For purposes of the AE summaries, the following will apply:

- AEs with unknown intensity will be treated as "severe" for the tabulations.
- AEs with unknown relationship will be treated as "related" for the tabulations.
- AEs with unknown seriousness will be treated as "serious" for the tabulations.

There will be no imputation of AE data for the data listings. All data will be listed as recorded in the CRFs.

Adverse events with onset (start date/time) after dosing in Treatment Period 1, up to and including the final Follow-up visit will be summarised by treatment period and overall for all subjects, including tabulations by causality and severity (mild, moderate and severe). All tabulations will be presented by SOC and Preferred Term (PT). Furthermore, separate listings of SAEs, AEs that led to discontinuation (DAEs) and AEs that led to death will be presented.

Adverse events will be listed by subject and treatment, including the following information: verbatim term, SOC, PT and lowest level term, start date/time, end date/time, time from last dose, causality, action taken, whether the AE was classified as serious and the outcome.

All tabulations will include the number and percentage of subjects. In addition, a separate tabulation will be presented showing the number of events by treatment and PT.

Finally, an overview of all AEs will be presented, separately for the number and percentage of subjects and the number of events. This will include categories for any AE, AEs with outcome of death and SAEs

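### By-treatment AE tables use windows of unequal length (about 4-5, at least 14, and 7-14 days) with crude counts; a supplementary 0-96 h table would equalise window length and residency, though not scheduled chemistry or period

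*Combined protocol and SAP*

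**What the plan says.** Section 10.1.1 assigns each AE to the treatment most recently dosed. The reference (verinurad+allopurinol alone) takes AEs starting at or "after dosing in Treatment Period 1 until the time of dosing in Treatment Period 2". The cyclosporine combination takes those starting at or "after dosing in Treatment Period 2 until the time of dosing in Treatment Period 3". The rifampicin combination takes those starting at or "after dosing in Treatment Period 3 until the Follow-up Visit".

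Section 3.1 sets the spacing. "There will be no washout between Treatment Period 1 and Treatment Period 2", and subjects stay in the unit throughout those two periods. "There will be a minimum washout period of 14 days between dosing in Treatment Period 2 and dosing in Treatment Period 3", with about 10 of those days spent outside the unit. Follow-up is 7 to 14 days after the last dose. The last PK sample in every period is at 96 hours (Table 3-1).

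The summaries in Section 10.1.1 are crude: "All tabulations will include the number and percentage of subjects", and "a separate tabulation will be presented showing the number of events by treatment and PT". Section 11.2.5 also calls for frequencies and proportions by treatment. No exposure-adjusted rate and no common-window table is planned. The AE listing will carry "start date/time, end date/time, time from last dose, causality" and other items, so the timing data will exist.

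**The concern.** The three columns of the by-treatment AE table cover different lengths of time, and the shortest belongs to the reference. A subject who goes on to Period 2 leaves the reference column after about 4 to 5 days, all in-house. The same subject then contributes at least 14 days under cyclosporine and 7 to 14 days under rifampicin, much of it as an outpatient. Crude counts and percentages do not allow for this, so the combinations can look less well tolerated with no drug effect at all.

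One illustration: Section 6.3.1.4 records confirmed and suspected SARS-CoV-2 infection as an AE. The post-dose days spent in the community, and the RT-PCR on Day -1 of Period 3, all fall in the combination windows.

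At stake is how a descriptive table reads. Safety and tolerability of the combinations is a secondary objective, with AE incidence among its outcome measures (Table 2-2). Section 11.2.1 says that no separate SAP will be written, so this protocol is the place to specify the table.

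A smaller, related gap is the denominator of the by-treatment percentages. The safety set is fixed by the Period 1 dose (Section 11.1.2), while 14 subjects are enrolled to secure 12 at the end (Section 11.4). Section 10.1.1 does not say which number is used in the later columns.

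**Working it through.** The documents give no figure for window length, so there is none to reproduce. The lengths are derived first.

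**Windows**
- Reference: at least 96 h = 4 days (last sample, no washout), or 5 days if the Period 2 dose is given the day after that sample.
- Cyclosporine: 14 days as a floor. Sections 3.1 and the Synopsis allow up to 36 days for the three periods. With one day for Day -1 and five for Period 3, the longest window is 36 - 1 - 4 - 5 = 26 days (4-day reference) or 36 - 1 - 5 - 5 = 25 days (5-day reference).
- Rifampicin: 7 to 14 days.
- Check: 14 - 4 (discharge at 96 h) - 1 (Day -1 check-in) = 9 non-resident days, in line with the roughly 10 in Section 3.1.

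**Expected event ratio to reference, no drug effect**

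Let W be the combination window in days and R the reference window (4 or 5). Let k be the AE rate in the first 96 h divided by the later rate, and q the fraction of outpatient AEs detected. Both k and q are assumptions, as the documents give neither.

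Ratio = [4k + q(W - 4)] / [4k + (R - 4)]

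| Assumption | Cyclosporine, W = 14 | Rifampicin, W = 7 to 14 |
|---|---|---|
| k = 1, q = 1 | 14/5 = 2.80 to 14/4 = 3.50 | 7/5 = 1.40 to 14/4 = 3.50 |
| k = 3, q = 1 | 22/13 = 1.69 to 22/12 = 1.83 | 15/13 = 1.15 to 22/12 = 1.83 |
| k = 5, q = 1 | 30/21 = 1.43 to 30/20 = 1.50 | 23/21 = 1.10 to 30/20 = 1.50 |
| k = 10, q = 1 | 50/41 = 1.22 to 50/40 = 1.25 | 43/41 = 1.05 to 50/40 = 1.25 |
| k = 1, q = 0.25 | 6.5/5 = 1.30 to 6.5/4 = 1.63 | 4.75/5 = 0.95 to 6.5/4 = 1.63 |
| k = 5, q = 0.25 | 22.5/21 = 1.07 to 22.5/20 = 1.13 | 20.75/21 = 0.99 to 22.5/20 = 1.13 |

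If the 36-day maximum were used, the cyclosporine ratio at k = 1, q = 1 would be 25/5 = 5.0 to 26/4 = 6.5.

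**Subjects with at least one AE**

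At a constant rate with full detection, if a proportion p have an AE in the reference window, 1 - (1 - p)^(W/R) have one in a window of W days. For p = 10% (assumed), the 14-day cyclosporine window gives 25.5% to 30.8% and the rifampicin window 13.7% to 30.8%. For p = 20%, the figures are 46.5% to 54.2% and 26.8% to 54.2%.

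In numbers of subjects, take 14 dosed in both columns and an assumed early rate r of 1% to 2% per day. Expected subjects = 14 × {1 - exp[-(4r + (days - 4)r/k)]}.
- k = 1: smallest excess 1.83 - 0.68 = 1.1 (r = 1%, R = 5, from unrounded values); largest 3.42 - 1.08 = 2.3 (r = 2%, R = 4).
- k = 5: smallest excess 0.82 - 0.58 = 0.2; largest 1.58 - 1.08 = 0.5.

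**What a common 0-96 h window equalises**

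Each column would cover 4 in-house days, so the expected ratio per subject dosed is 4/4 = 1.0 for any rate shape common to the three periods, provided detection is equal. Table 3-1 shows where it is and is not equal:
- Vital signs and Day 3 haematology are scheduled alike in all three periods.
- Post-dose chemistry within 96 h is scheduled only in Period 1 (Days 1, 2 and 3, limited analytes). After the Period 2 and Period 3 doses, the next chemistry is at Period 3 Day -1 and at Follow-up. The four full and three small chemistry samples in Table 7-1 fit this.
- The only scheduled post-dose ECG is at Follow-up.

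**Denominator**: one subject is 1/14 = 7.1% or 1/12 = 8.3%.

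**The case against.** The strongest defence is that nothing here is an error. The rule is complete, simple and keeps every AE. The PK outcomes are defined relative to the reference, whereas the safety outcome is only AE incidence, with no contrast or test. With 14 subjects and time from last dose in the listing, a reader can rebuild any window. All of that stands, and it limits the point to how a descriptive summary reads. It does not make the summary comparable: columns set side by side by treatment will be compared, and a listing does not correct a percentage.

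Four stronger readings are tempting, and the documents do not support them.
- A reader might infer that late AEs can never reach the reference column. A subject withdrawn after Period 1 has no Period 2 dose to close the window. Section 10.1.1 also moves an AE with a missing start day to the first dosing day of that month, which can be the Period 1 dose.
- A reader might infer that a 0-96 h table is fully like-for-like. It is not for AEs found by chemistry, because of the schedule above. This matters because Section 3.3 names creatinine elevation as the main toxicity concern with verinurad monotherapy.
- A reader might take the threefold ratio as the expected result. It rests on a constant rate and full detection. Conversely, 25% outpatient detection has no support in the documents, since subjects are asked about AEs at Period 3 Day -1 and at Follow-up.
- A reader might dismiss late AEs as background because 96 h is 96/13 = 7.4 verinurad half-lives and 96/6 = 16 cyclosporine half-lives. Those half-lives may not hold with an inhibitor present, and none is given for rifampicin, oxypurinol, M1 or M8. Late AEs must therefore stay visible.

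**Conclusion.** The point holds as a cheap improvement to a descriptive analysis. For subjects who continue to Period 2, the windows are about 4 to 5 days (derived), at least 14 days, and 7 to 14 days. Crude counts therefore favour the reference whenever later AEs occur and are detected.

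The direction follows from the plan, but the size does not. It runs from 2.8-3.5 (cyclosporine, 14-day minimum) and 1.4-3.5 (rifampicin) at a constant rate with full detection, down to about 1 with early clustering and low outpatient detection. The rifampicin excess can vanish. The cyclosporine excess can be small, or larger than shown if the washout runs beyond 14 days.

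No formal decision depends on this table, and the primary PK analysis is unaffected.

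**What to change.** In Section 10.1.1, keep the full-window table and the listing, and add a supplementary table specified along these lines:
- AEs with onset from dosing to 96 hours after dosing, or to the next dose if earlier, are tabulated by treatment as number and percentage of subjects and number of events.
- AEs with later onset appear in a separate washout/follow-up column.
- The denominator is the number of subjects dosed in that period.
- AEs with a missing start day are shown separately and are not imputed into the 0-96 h column.
- A footnote says that the table equalises window length and residency but not scheduled chemistry, so AEs detected by laboratory chemistry should be read from the full-window table. It adds that treatment remains confounded with period because the sequence is fixed.

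It would also help to state which column takes later AEs of a subject withdrawn after Period 1.

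The cost is wording and one extra table from data already collected. The downside is that late-onset and chemistry-detected AEs on the combinations will sit mainly in the separate column, which is why the full-window table must stay.

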5.4.3. Dose and Treatment Regimens

Subjects will receive single oral doses of verinurad, allopurinol, cyclosporine and rifampicin in the following Treatment Periods under fasted conditions.

• Treatment Period 1: 7.5 mg verinurad and 300 mg allopurinol, fasted state (>10 h)

- Treatment Period 2: 7.5 mg verinurad, 300 mg allopurinol and 600 mg cyclosporine, fasted state (>10 h)
- Treatment Period 3: 7.5 mg verinurad, 300 mg allopurinol and 600 mg rifampicin, fasted state (>10 h)

The dose will be administered after an overnight fast of at least 10 hours and will be taken with 240 mL of water.

Subjects will be allowed to drink water to prevent dehydration until 1 hour before dosing.

Water will be allowed ad libitum from 1 hour after dosing and a standard meal will be given 4 hours after dosing.

After dosing, subjects will remain semi-supine on their bed or sitting (except when necessary for study procedures) until completion of the 4 hour vital sign assessments.

Subjects will receive the following IMPs in each Treatment Period, respectively:

Table 5-2 IMP in each Treatment Period

Treatment Period	IMP	Formulation	Dose
Period 1	Verinurad	Capsule	1 x 7.5 mg
	Allopurinol	Tablet	1 x 300 mg
Period 2	Verinurad	Capsule	1 x 7.5 mg
	Allopurinol	Tablet	1 x 300 mg
	Cyclosporine	Soft Capsule	6 x 100 mg
Period 3	Verinurad	Capsule	1 x 7.5 mg
	Allopurinol	Tablet	1 x 300 mg
	Rifampicin	Film coated Tablet	1 x 600 mg

Other restrictions, including posture control are described in Section 29. Data of subjects may be excluded from the PK analysis set as described in Section 11.1.3.

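### At the minimum washout, the rule for AEs with a missing start day would tabulate about 60-66% of affected cyclosporine-period events under verinurad+allopurinol alone

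*Combined protocol and SAP*

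**What the plan says.** Section 10.1.1 ties treatment to onset: "Adverse events will be assigned to a treatment based on the start date/time of the AE in relation to dosing in that treatment period". Period 1 runs to the Period 2 dose, Period 2 to the Period 3 dose, and Period 3 to Follow-up.

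For incomplete start dates the section gives these rules:

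- Day missing, in a month with dosing: "then the day will be imputed with the first day on which IMP was administered in that month". The only check is against the end date: "If this results in a start date after the end date, then the day will be imputed with the first day of the month".
- Time missing on a dosing date: "In this case the start time will be imputed with the time of dosing". An imputed dosing day therefore falls inside the period that the dose opens.
- Month missing, in a year with dosing: the first dosing month is used.
- Day and month missing, in a year with dosing: "then the day and month will be imputed with the day and month of dosing".
- Nothing known: "Adverse events with completely unknown start dates will be imputed with the date and time of dosing", unless the end date precedes dosing.

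The same section counts unknown intensity as severe, unknown relationship as related and unknown seriousness as serious. It does not impute the listings. Sections 3.1 and 5.4.3 fix the sequence as verinurad+allopurinol alone, then with cyclosporine, then with rifampicin. On the first transition Section 3.1 states: "There will be no washout between Treatment Period 1 and Treatment Period 2".

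**The concern.** The rule is explicit and can be programmed, and its result depends on the calendar rather than on when the event was likely to have started. In a month that contains the Period 1 dose, the first dosing day is always the dose without an inhibitor. The end-date check can only move the start earlier. No rule uses the visit or the collection period to place an event later.

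Partial dates are most likely outside the unit. Subjects are resident through Periods 1 and 2 and to Day 5 of Period 3. The out-of-unit days are therefore the washout days (cyclosporine window) and the days from Period 3 discharge to Follow-up (rifampicin window). None belongs to Period 1.

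The safety objective concerns the combinations. With 12 to 14 subjects, one event is 1/14 = 7% to 1/12 = 8% of a column. Moving an uncertain event to the no-inhibitor column also runs against the worst-case rules in the same section.

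Separately, two rules refer to dosing as if there were one dose. Each subject has three, so the programmer must make a choice that the plan does not state. Section 11.2.1 says no separate SAP will be written.

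**Working it through.** The plan gives no figure on this point, so the rule was applied to the planned calendar.

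**Inputs**

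- Period 1 dose on day d, taken as each date from 1 July to 31 August 2020. The synopsis gives July to September 2020, and dosing to Follow-up takes at least 4 + 14 + 7 = 25 days.
- Period 2 dose on d+4. This is inferred from Days 1 to 5, 96-hour sampling and no washout.
- Period 3 dose on d+18 (14-day minimum, Section 3.1). As a sensitivity case, d+30: counting Day -1 to Day 5, the 36-day maximum allows 36 - 1 - 4 - 5 = 26 days between the doses.
- Follow-up 7 or 14 days after the last dose.
- Assumption: onset equally likely on each day, either over all days or over out-of-unit days only.

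**Formula.** July and August both have 31 days. An event on day d+k falls in the month of the Period 1 dose for 31 - k of every 31 start dates (none once k reaches 31). Whenever it does, the rule credits Period 1. The share credited to the reference is the mean of (31 - k)/31 over the days concerned.

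| True period | Days k | Share credited to Period 1 |
|---|---|---|
| Cyclosporine, all days | 4-17, mean 10.5 | 20.5/31 = 66% |
| Cyclosporine, out of unit | 9-16, mean 12.5 | 18.5/31 = 60% |
| Cyclosporine, 26-day gap, all | 4-29, mean 16.5 | 14.5/31 = 47% |
| Cyclosporine, 26-day gap, out | 9-28, mean 18.5 | 12.5/31 = 40% |
| Rifampicin, all, Follow-up day 7 | 18-25, mean 21.5 | 9.5/31 = 31% |
| Rifampicin, all, Follow-up day 14 | 18-32 | 91/465 = 20% |
| Rifampicin, out, Follow-up day 7 | 23-25, mean 24 | 7/31 = 23% |
| Rifampicin, out, Follow-up day 14 | 23-32 | 36/310 = 12% |
| Rifampicin, 26-day gap | from 30 | at most 1/248, rounds to 0% |

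(91 = 13 + 12 + ... + 1; 36 = 8 + 7 + ... + 1; 465 = 15 × 31; 310 = 10 × 31; 248 = 8 × 31.)

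**Who is in the Period 1 column.** Per 31 start dates, the day-missing onsets credited to Period 1 are:

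- from Period 1: 31 + 30 + 29 + 28 = 118;
- from Period 2: 14 × 20.5 = 287;
- from Period 3: 8 × 9.5 = 76 (Follow-up day 7) or 91 (day 14).

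The combination share is 363/481 = 75% to 378/496 = 76%. If partial dates arise only out of the unit, it is 100%.

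**Movement the other way.** A cyclosporine-period event in a month after the Period 2 dose month goes forward to Period 3 if no end date limits it. The mean of (k - 4)/31 is 6.5/31 = 21% (all days) or 8.5/31 = 27% (out of unit). With a 26-day gap it is 12.5/31 = 40% or 14.5/31 = 47%. If the event ends a day after onset, the shift falls to 0-3%.

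**Sensitivity.** With the Period 2 dose on d+5 and the 14-day gap, the reference receives 56-63% of cyclosporine-period and 9-27% of rifampicin-period events. The combination share becomes (273 + 68)/(145 + 273 + 68) = 70% to (273 + 78)/(145 + 273 + 78) = 71%.

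**The case against.** The strongest reply is that few events will be affected. Start date and time are collected for each AE (Section 6.3.1.4). Subjects are questioned at every visit, including Day -1 of Period 3 (Table 3-1), about the time since they were last asked. Missing data are taken up with the Investigator (Section 9.4.1), and queries repeat until resolved (Section 9.5). Listings show the date as recorded, the overall AE summary does not change when an event moves between periods, and the safety analysis is descriptive. All of this stands, and it limits the size of the problem. It does not justify the default.

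Some stronger readings are tempting, but the documents do not support them:

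- That inhibitor-period events in general go to the reference. Most day-missing rifampicin-period events (56-76%) stay in Period 3 at the 14-day gap, and practically none go to Period 1 at 26 days.
- That the error runs only toward the reference. Some cyclosporine-period events move forward to rifampicin, as shown above.
- That 84-88% of events in the Period 1 column would be misplaced, because Period 1 covers only 4 of 25 to 32 days at risk. This ignores month boundaries: events in later months cannot be imputed to the Period 1 dose.
- That the wholly-unknown and day-and-month rules also favour Period 1. They do not say which dose applies. That is an ambiguity, and a period-specific reading is possible.

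**Conclusion.** The point holds for the day-missing rule. At the minimum washout, a day-missing event from the cyclosporine period is more likely than not to be tabulated under verinurad+allopurinol alone (60-66%). The share falls to 40-47% if the washout stretches to 26 days. For the rifampicin period it is a minority result (12-31%, or 0% after rounding). About three quarters of the day-missing events placed in Period 1 would belong to a combination.

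These figures rest on uniform onset, the inferred 4-day interval between the first two doses and the planned July-August dosing dates. They are shares of partly dated events. The documents give no expected count of those, so no effect on overall AE rates can be stated. The consequence is confined to the by-treatment AE tables. This is a minor but clear-cut correction, and the two rules that leave the dose undefined need completing in any case.

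**What to change.** Replace the partial-date rules in Section 10.1.1 with one rule. A missing or partial start date is imputed to the dosing date/time of the latest Treatment Period compatible with (a) the known parts of the date, (b) the end date and (c) the visit at which the AE was first reported. An AE first reported before the Period 3 dose cannot be assigned to Period 3, and likewise for Period 2. The same rule applies when the start date is wholly unknown. Keep the existing exception for events that ended before dosing, and state that it means the Period 1 dose.

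Condition (c) is essential. Without it, and with no limiting end date, a cyclosporine-period event goes to rifampicin whenever its month contains the Period 3 dose. That share is the mean of 1 - (18 - k)/31, which is 1 - 7.5/31 = 76% over all days and 1 - 5.5/31 = 82% out of the unit. With it, any such event reported by Day -1 of Period 3 stays in Period 2, and no Period 2 or 3 event defaults to Period 1.

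The cost is a short text change and a small programming change. The visit of first report is not among the AE variables in Section 6.3.1.4, so it must be added or derived from the electronic source record. The downside is that some uncertain events, chiefly those reported late, will be over-attributed to a combination. That matches the section's worst-case handling of intensity, relationship and seriousness.
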